10.5.3 Safety Analysis

The primary objective of the study is the evaluation of the safety and tolerability of ARCT-021. The primary endpoints that align with this objective are:

- Solicited AEs for 7 days after vaccination (Cohort 1), summarized by toxicity grade
- Unsolicited AEs for 28 days after vaccination (Cohort 1), summarized by mild/moderate/severe and relationship to ARCT-021
- SAEs through Day 197 (Cohort 2; 12 months after ARCT-021 vaccination in ARCT-021-01 study), summarized by relationship to ARCT-021
- SAEs through Day 365 (Cohort 1; 12 months after ARCT-021 vaccination in ARCT-021-02 study), summarized by relationship to ARCT-021
- MAAEs through Day 197 (Cohort 2; 12 months after ARCT-021 vaccination in ARCT-021-01 study), summarized by relationship to ARCT-021
- MAAEs through Day 365 (Cohort 1; 12 months after ARCT-021 vaccination in ARCT-021-02 study), summarized by relationship to ARCT-021
- NOCDs through Day 197 (Cohort 2; 12 months after ARCT-021 vaccination in ARCT-021-01 study), summarized by relationship to ARCT-021
- NOCDs through Day 365 (Cohort 1; 12 months after ARCT-021 vaccination in ARCT-021-02 study), summarized by relationship to ARCT-021
- Safety laboratory assessments through 28 days after vaccination (Cohort 1), summarized by toxicity grade (where relevant)

- Vital signs assessments through day 365 (Cohort 1; 12 months after ARCT-021 vaccination in ARCT-021-02 study) summarized by toxicity grade

To support the continued characterization of ARCT-021 tolerability and safety when administered as a single dose, the following summaries will be provided:

- Summary of solicited (7 days after vaccination) and unsolicited AEs 28 days after vaccination)
- Summary of MAAEs, NOCDs, SAEs through 12 months after vaccination

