5.4 Handling of Dropouts or Missing Data

Due to the exploratory nature of this study and the lack of statistical testing, missing data will not be imputed. Values that are below the level of quantification will be recoded to zero for analysis purposes, with the exception of antibody titers which will be recoded to LLOQ/2.

For participants who received an off-study vaccine, Safety and Immunogenicity reports will be censored at date of first dose of off-study vaccine. Safety data after off-Study vaccine will be reported separately.

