8. SAFETY ANALYSIS

The primary objective of the study is the evaluation of the safety of ARCT-021. The primary endpoints that align with this objective are:

- Solicited AEs for 7 days after vaccination with ARCT-021 (Cohort 1 only).
- Unsolicited AEs within 28 days after vaccination with ARCT-021 (Cohort 1 only), summarized by mild/moderate/severe and relationship to ARCT-021.
- SAEs, MAAEs, NOCD and AE leading to discontinuation/withdrawal according to the following windows
 - Pre-Study for cohort 1b
 - Within 28 days after vaccination with ARCT-021 (Cohort 1 only)
 - from 28 days after vaccination to the last observation prior to receipt of off study vaccine or prior the data cut point for this interim, whichever is first (all cohorts/sub-cohorts).
- Safety laboratory assessments through 28 days after vaccination with ARCT-021 (Cohort 1 only), summarized by toxicity grade (where relevant).
- Vital signs assessments through the last observation prior to receipt of off study vaccine or prior to the data cut point for this interim, whichever is first, summarized by toxicity grade.
- Unsolicited AEs, MAAEs, SAEs and vital signs assessments from after receipt of off-study vaccine up to the observation prior to the data cut point for this interim.

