8.1.9.1 Unsolicited Adverse Event Summaries

All unsolicited AEs (serious and non-serious) occurring after exiting Parent study and after administration of first dose of study vaccine (in this study or parent study as applicable) and before the End of Study or Off-study vaccination, regardless of relationship to study vaccine, will be included and classified by system organ class (SOC) and preferred term (PT) using the Medical Dictionary for Regulatory Activities (MedDRA).

- For Cohort 1a, AE occurring from the time of exiting the Parent Study up to receipt of Study Vaccine on Day 1 will be regarded as medical history. All unsolicited events, including SAEs, MAAEs, and NOCD are collected up to 28 days after receipt of study vaccine and only SAEs, MAAEs, and NOCD are collected beyond 28 days after receipt of study vaccine.
- For Cohort 1b, SAEs, MAAEs, and NOCD occurring from the time of exiting the Parent Study up to receipt of study vaccine on Day 1 will be regarded as treatment emergent but will be presented separately (as 'Pre-Study TEAEs') to TEAEs occurring after receipt of vaccine. All unsolicited events, including SAEs, MAAEs, and NOCD are collected up to 28 days after receipt of study vaccine in Study ARCT-021-02 but only SAEs, MAAEs, and NOCD are collected beyond 28 days after receipt of study vaccine.
- For Cohort 2 only SAEs, MAAEs, and NOCD are collected in Study ARCT-021-02 as no further study vaccine is administered in this study. All events reported from the time of exiting the Parent Study up to the data cut point for this interim analysis are regarded as treatment emergent and will be presented merged for the purposes of tabulation.

Solicited systemic and local adverse events will not be included in the unsolicited AE summaries, unless the solicited AE has onset >7 days after administration of Study vaccine or the solicited event is serious or medically attended.

Unsolicited AEs that appear within the Toxicity Grading Scale for Healthy Adult and Adolescent Volunteers Enrolled in Preventive Vaccine Clinical Trials, Sept 2007 will have been entered in the EDC with a numerical Grade (1 to 4). Unsolicited TEAEs that are not contained within this scale will have been graded as mild/moderate/severe. For the purposes of tabulation of unsolicited AEs, events will be presented as mild/moderate/severe, whereby the CRF-designated Grade 1 = mild, Grade 2 = moderate and \geq Grade 3 = severe.

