- ii. the number and percentage of participants experiencing a solicited event by Systemic vs Local and by event term, day post vaccination (from Day 1 to Day 7, where Day 1 is the day of injection), by age groups, and the maximal severity. The number and percentage of participants experiencing a solicited event, by event term, by age group, occurring at any time from Day 1 to Day 7 will also be displayed.

The age groups referenced above are all participants, 21 to 55 years, and 56 to 80 years at the time of enrollment in the Parent Study. Cohort/sub-cohorts are described in Section [5.2](#).

8.1.9.3 Adverse Events After Off-Study Vaccine.

- i. An overall summary of unsolicited treatment emergent adverse events with onset after injection of off-study vaccine, longitudinal Safety population which includes, by age group:
 - a. the number and percentage of participants experiencing an AE leading to study withdrawal
 - b. the number and percentage of participants experiencing a SAE by maximal severity
 - c. the number and percentage of participants experiencing an MAAE
 - d. the number and percentage of participants experiencing a NOCD

The age groups referenced above are all participants, 21 to 55 years, and 56 to 80 years at the time of enrolment in the Parent Study.

NOTE: unsolicited AE that are not SAE, MAAE or NOCD are not collected in this study for participants in cohort 2 and are only collected up to 28 days after injection of ARCT-021 for participants in cohorts 1a and 1b. No participants received an off-study vaccine within the time window for collection of unsolicited AE that are not SAE, MAAE or NOCD, so no tabulation of all unsolicited events is being provided.

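### No summary table in the interim SAP gives SAEs, MAAEs and NOCDs by relationship to ARCT-021 and by cohort regardless of off-study vaccination, as protocol 10.5.3 specifies

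*SAP*

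**What the plan says.** **Protocol 10.5.3** lists the primary safety endpoints by cohort, to a fixed day and by relationship. For Cohort 1 it gives "SAEs through Day 365 (Cohort 1; 12 months after ARCT-021 vaccination in ARCT-021-02 study), summarized by relationship to ARCT-021", and for Cohort 2 "MAAEs through Day 197 (Cohort 2; 12 months after ARCT-021 vaccination in ARCT-021-01 study), summarized by relationship to ARCT-021". The other SAE, MAAE and NOCD entries follow the same pattern. None of them mentions another vaccine.

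**SAP 5.4** states that for participants given an off-study vaccine, "Safety and Immunogenicity reports will be censored at date of first dose of off-study vaccine", with later safety data reported separately. SAP 3.1, 5.3.3 and 8.1 say much the same. SAP 5.3.3 gives the reason: a similar vaccine could cloud interpretation.

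**SAP 8** restates the primary endpoints. It keeps the relationship summary for 28-day unsolicited AEs, but not for SAEs, MAAEs and NOCDs. Beyond 28 days their window runs "to the last observation prior to receipt of off study vaccine or prior the data cut point for this interim", whichever is first.

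**SAP 8.1.9.1** restricts the main unsolicited-AE tables to events after parent-study exit and after first study vaccine "and before the End of Study or Off-study vaccination, regardless of relationship to study vaccine, will be included". Relationship appears in rows i.b and i.d and in tables iii and iv, always for TEAEs as a whole. Rows i.g, i.h and i.i count SAEs, MAAEs and NOCDs without a relationship split.

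**SAP 8.1.9.3** is the only table for events after off-study vaccine. Its four rows are AEs leading to withdrawal, "the number and percentage of participants experiencing a SAE by maximal severity", MAAEs and NOCDs, all by age group.

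**The concern.** The protocol's long-term question is how many participants in each cohort had an SAE, MAAE or NOCD over 12 months, and in how many the event was judged related to ARCT-021. The SAP answers a narrower question, because its relationship tables cover only the period before any off-study vaccine. The two sets of tables also cannot be put back together: one is by cohort with relationship, the other by age group without it.

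A late-onset condition that the investigator judges related to ARCT-021, but that starts after another vaccine, would not be counted as related in any summary table. The one-year follow-up exists to capture such events. The analysis supports a regulatory filing (SAP 4), where summary tables are likely to be read first.

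**Working it through.** The plan has no figure to reproduce. Protocol 10.1 says that formal sample size calculations do not apply. The check is a comparison of outputs.

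**Step 1. Does any output have all the features of the protocol endpoint?**

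| Output | SAE, MAAE, NOCD shown separately | By relationship | By cohort | Includes events after off-study vaccine | Summary table |
|---|---|---|---|---|---|
| Protocol 10.5.3 | yes | yes | yes | yes (no cut-off stated) | yes |
| SAP 8.1.9.1 i.g–i.i | yes | no | yes | no | yes |
| SAP 8.1.9.1 i.b, i.d, iii, iv | no (all TEAEs) | yes | yes | no | yes |
| SAP 8.1.9.3 | yes | no (0 of 4 rows) | no (age group) | only these | yes |
| SAP 8.1.4–8.1.6 listings | yes | yes | yes | yes (no cut-off stated) | no |

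No row of the SAP matches the protocol row. The SAE, MAAE and NOCD rows lack relationship even before off-study vaccination, so censoring is only part of the cause.

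**Step 2. Can the endpoint be rebuilt from the tables?** No. 8.1.9.3 has no cohort or relationship split. Both tables also count participants, and one person can appear in each, so the counts cannot simply be added.

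**Step 3. Which endpoints does the censoring affect?** The note in SAP 8.1.9.3 says that no participant had an off-study vaccine inside the window for collecting other unsolicited AEs. The 28-day AE tables are therefore untouched, and among AE endpoints the censoring falls on SAEs, MAAEs and NOCDs. SAP 5.3.3 also provides for off-study doses completed before enrolment. Exclusion criterion 3 in protocol 5.2 binds only subjects who will receive ARCT-021 here, so this can arise in Cohort 2. Any such participant has all in-study follow-up outside the relationship tables.

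**Step 4. Direction.** Fix a cohort of N participants, an event type and a follow-up horizon. Let R be the participants with at least one such event judged related, and R_c those with at least one that began before off-study vaccine.

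- R_c is a subset of R.
- SAP 8.1.9.1 divides by all participants in the cohort for the tables after the overall summary. It states no other denominator for the overall summary, and no adjustment for shortened follow-up.
- Hence |R_c|/N ≤ |R|/N. The two are equal only if nobody's related events of that type all began after off-study vaccination.

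**Step 5. Size.** This needs the number vaccinated off study, when, and the data-cut date. SAP 5.3.3 says only that off-study vaccination happened in many cases. The other two are not stated, so no figure follows.

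**Step 6. Is the change declared?** SAP 4 says that it summarises changes from the protocol's analyses. Sections 4.1 to 4.4 cover cohort names, day calculation, assays, the seroconversion definition and data availability. Off-study censoring of safety endpoints is not among them.

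**The case against.** The strongest reply is that a reader might infer more than the documents show.

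- **That the 12-month endpoint is never produced.** This is not supported. The SAP covers an unplanned interim analysis and stops at a data cut, and protocol 10 foresees a SAP finalised before final database lock. No final SAP is among the documents. SAP 8.1.9.1 and 8.1.9.2 do say that their tables are presented at the final analysis, but SAP 4.4, 8 and 8.1 set the window at the interim cut. That wording needs clarifying and does not show that an endpoint was abandoned.
- **That later events are dropped.** They are not. SAP 8.1.9.3 counts them, and participants without off-study vaccine stay in the relationship tables throughout. Deaths lack their own row in 8.1.9.3, but death is an SAE criterion, so they fall in the SAE row.
- **That relationship is lost.** It is not. The SAE, MAAE and NOCD listings carry relationship and onset date by cohort, and narratives are required for each event. In a descriptive study of about 106 participants this has real value. In Cohort 2 only SAEs, MAAEs and NOCDs are collected, so row i.b already gives their pooled relationship split up to off-study vaccination.
- **That the censoring is hidden or unreasonable.** It is stated in several places, with a sensible reason. An uncensored table will include events possibly due to the other vaccine.

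All of this stands, and it limits the point to summary tables. It does not remove it. The protocol specifies a summary, a listing is not one, and interim status does not explain why a table meant for a filing omits a split that the protocol attaches to a primary endpoint.

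**Conclusion.** The point holds for this interim SAP. No summary table shows SAEs, MAAEs and NOCDs, each by relationship and by cohort, regardless of off-study vaccine. After off-study vaccination, relationship is left to listings and narratives.

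The effect on the tabulated incidence of events judged related is one-sided (equal or lower) against the protocol definition at the same horizon. This assumes that the denominator stays the full cohort, as SAP 8.1.9.1 indicates. It refers to the investigator's relationship judgement and does not show that events truly caused by ARCT-021 are undercounted.

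The size is unknown. A reader might put a number on it by assuming uptake u at Day t and computing u × (365 − t)/364 for Cohort 1. Assumed values of 30% at Day 270 and 70% at Day 90 give 0.3 × 95/364 = 8% and 0.7 × 275/364 = 53%. These are shares of 12-month person-time under invented inputs. They do not describe this data cut or Cohort 2, and they are not shares of missing events, because 8.1.9.3 counts those events.

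The point merits correction because the missing summary belongs to the protocol's own primary endpoint and the data exist.

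**What to change.** 1. In SAP 8.1.9.3, add splits by relationship to ARCT-021 and by cohort.
2. In SAP 8.1.9.1, add one table per cohort (1a, 1b and 2) of SAEs, MAAEs and NOCDs, each by relationship and regardless of off-study vaccine. Run it to the data cut at this interim and to Day 365 (Cohort 1) or Day 197 (Cohort 2) at the final analysis. Show it beside the censored table.
3. In SAP 4.3, list the off-study censoring of safety endpoints as a change from protocol 10.5.3.

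The cost is SAP wording, two added splits and one extra table. Relationship is already recorded for each event. The drawback is that the new table includes events that may be due to the other vaccine. The relationship split and the adjacent censored table make these visible.

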8.2 Clinical Laboratory Assessments

Laboratory tests including chemistry panel, complete blood count with differential, coagulation panel, lipid panel, and urinalysis will be summarized by study visits for Safety population.

For lab parameters contained within the Toxicity Grading Scale for Healthy Adult and Adolescent Volunteers Enrolled in Preventive Vaccine Clinical Trials, Sept 2007 that have worsening of toxicity grade findings within 7 days of vaccination, will be summarized in shift tables which will include grade at baseline and maximum grade after Study vaccine administration.

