Statistical Considerations	
Sample Size
 
As this is an open label follow-on study, the sample size is determined by the number of subjects enrolled in the Parent Study who consent to enroll in this study and fulfill the eligibility criteria; therefore, formal sample size calculations are not applicable.
 
Safety and Tolerability
 
For subjects who received ARCT-021 in the Parent Study, SAE, MAAE, CESI, NOCD occurring since completion of the Parent Study and the Screening visit for this study will be recorded in the EDC to ensure continuity of safety follow-up from the Parent Study to this study.
 
Subject incidence rates of all treatment emergent adverse events (TEAEs) will be tabulated by MedDRA system organ class, and by preferred term. TEAEs will also be summarised by relationship to Study Drug, seriousness, and severity. Injection site and systemic (fever, fatigue, headache, chills, nausea, vomiting, diarrhoea, new or worsened myalgia, and new or worsened arthralgia) solicited adverse events will be summarised separately and solicited events with onset within 7 days of injection will be considered related. Tables and/or narratives of treatment emergent deaths, serious and significant adverse events, including early withdrawals due to adverse events, will also be provided.
 
Laboratory tests including chemistry panel, complete blood count with differential, coagulation panel, etc., will be summarised by study visit.
 
Vital sign measures will be tabulated. In addition, the number of subjects who experience abnormalities in clinical laboratory evaluations will be summarised by grade (Section 9.4.4.2).
 
The severity of AEs and SAEs will be graded according to the Toxicity Grading Scale for Healthy Adult and Adolescent Volunteers Enrolled in Preventive Vaccine Clinical Trials, Sept 2007.
 
Any AE not listed in this scale will be graded as follows:

[figure not shown]

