9.5 Procedures for Handling Special Situations

9.5.1 Abnormalities of Laboratory Tests

Clinically significant abnormal laboratory test results may, in the opinion of the Investigator, constitute or be associated with an AE. Examples of these include abnormal laboratory results that are associated with symptoms, or require treatment, e.g., bleeding due to thrombocytopenia, tetany due to hypocalcemia, or cardiac arrhythmias due to hyperkalemia. Whenever possible, the underlying diagnosis should be listed in preference to abnormal laboratory values as AEs. Clinically significant abnormalities will be monitored by the Investigator until the parameter

returns to its baseline value or until agreement is reached between the Investigator and Sponsor Medical Monitor (or designee) that further follow-up is not required. Laboratory abnormalities deemed not clinically significant (NCS) by the Investigator should not be reported as AEs. Similarly, laboratory abnormalities reported as AEs by the Investigator should not be deemed NCS on the laboratory sheet.

The Investigator is responsible for reviewing and signing all laboratory reports. The signed clinical laboratory reports will serve as source documents and should include the Investigator's assessment of clinical significance of out of range/abnormal laboratory values.

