2.2 Endpoints

2.2.1 Primary Endpoint

The safety and reactogenicity of ARCT-021 will be assessed by determining the incidence, severity, and dose-relationship of solicited local and systemic adverse events, unsolicited adverse events (including serious adverse events (SAEs)), and changes in Laboratory Toxicity Results.

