4. CHANGES TO PLANNED ANALYSIS

This is an unplanned interim analysis that was not anticipated at the time of study initiation and is being conducted to support a regulatory filing in [REDACTED] and other jurisdictions, as applicable. In addition, based on data availability in specific subgroups of participants in this study, further adjustments in the original protocol-specified analyses are made. These additional changes from the analyses described in the protocol are summarized below.

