5.1 Data Quality Assurance

Efforts were made to perform source data verification, query resolution and data base lock prior to conducting the interim analysis. However, this is an unplanned interim analysis to support a regulatory filing that was not anticipated at the time of study initiation, and due to the short timeline, it was not possible to complete these activities. Therefore, data are to be pulled by CTI Biostatistics for interim analyses at a time when source verification and query resolution is still ongoing.

No changes will be made to this interim analysis SAP after the data is pulled for analysis.

All SAS programs used to create analysis data sets, tables, and listings are double programmed. The SAS outputs will be compared and the programs will be updated until the outputs match. Statistical outputs will be reviewed for consistency with the shells, accuracy, and consistency across outputs by a senior member of the Biostatistics team.

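### SAP 8.2 admits laboratory parameters to the toxicity-grade shift tables only if they worsen within 7 days, although the primary laboratory endpoint runs through 28 days

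*SAP*

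**What the plan says.** The SAP lists among its primary safety endpoints "Safety laboratory assessments through 28 days after vaccination with ARCT-021 (Cohort 1 only), summarized by toxicity grade" (Section 8), where relevant. Protocol 10.5.3 has the same endpoint: "Safety laboratory assessments through 28 days after vaccination (Cohort 1), summarized by toxicity grade". SAP 2.2.1 includes "changes in Laboratory Toxicity Results" in the primary endpoint. The statistical part of the protocol synopsis requires that "the number of subjects who experience abnormalities in clinical laboratory evaluations will be summarised by grade" and sets no 7-day limit.

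SAP 8.2 is where the laboratory analysis is specified. It plans two outputs for the Safety Population:

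- Laboratory tests summarized by study visit, with no statement that these summaries are by grade.
- For parameters on the vaccine toxicity grading scale, those with "worsening of toxicity grade findings within 7 days of vaccination, will be summarized in shift tables". Each table sets the baseline grade against the maximum grade after vaccination, and no end day is given for that maximum.

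SAP Section 4 introduces its list of departures with "These additional changes from the analyses described in the protocol are summarized below". A 7-day limit on laboratory grading is not in that list.

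**The concern.** The endpoint and the display meant to deliver it use different windows. A 28-day endpoint by toxicity grade needs a graded table that responds to worsening at any time in those 28 days. The only graded table in SAP 8.2 responds to the first 7.

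Laboratory toxicity is a real question for this product. Table 2 of the protocol relies on liver tests monitored for 28 days after dosing as a mitigation. Protocol 2.3 reports reversible, asymptomatic grade 3 lymphopenia at this dose in the parent study, without stating its timing. According to SAP Section 2 the primary endpoints are evaluated at this interim, and according to SAP Section 4 the interim supports a regulatory filing. A reader of the shift tables could take the absence of a parameter to mean that its grade did not worsen over 28 days, when it means only that its grade did not worsen in the first week.

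**Working it through.** The plan gives no figure to reproduce. The check sets the scheduled draws against the two windows.

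**Inputs.** The schedules of assessments (protocol Appendix 1, SAP Appendix A) give these post-dose visits for participants injected in this study: Day 8 (±1), Day 15 (±1) and Day 29 (window 0). Chemistry and hematology are drawn at all three, urinalysis at Days 8 and 29 only. Coagulation has no scheduled draw after Day 1. The injection is on Day 1.

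**Formula.** Days after injection = study day − 1.

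| Visit | Permitted study days | Days after injection | At most 7 elapsed days | Study day 7 or earlier | At most 28 days |
|---|---|---|---|---|---|
| Day 8 | 7, 8, 9 | 6, 7, 8 | yes, yes, no | yes, no, no | all yes |
| Day 15 | 14, 15, 16 | 13, 14, 15 | all no | all no | all yes |
| Day 29 | 29 | 28 | no | no | yes |

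**Two day counts.** SAP 8.2 does not say how the 7 days are counted. SAP 8.1.9.2 uses two forms for solicited events: onset up to 7 days after injection, and days numbered 1 to 7 with the injection on Day 1. Neither is stated to apply to laboratory data, so both are shown.

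**Results.**

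- Chemistry and hematology draws that can never trigger entry, under either count: 2 of 3 = 67%. The earliest Day 15-visit draw is 13 days after injection, 13 − 7 = 6 days past the limit.
- Day 8 visit: 2 of its 3 permitted days qualify by elapsed days (Days 7 and 8), and 1 of 3 by numbered days (Day 7 only). On the second count a draw on the nominal Day 8 fails as well.
- Urinalysis: the Day 29 draw, 1 of its 2 post-dose draws, can never trigger entry.
- Every one of these draws falls within the 28-day endpoint.

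**What the limit removes.** As worded, the condition selects parameters. Once a parameter qualifies, its table shows the maximum grade after vaccination, so Day 15 and Day 29 values for that parameter can appear. The gap on this reading is any parameter with no worsening inside the limit and a first worsening later. The sentence is not well formed and could also be programmed as a filter on participants. In that case each participant's late first worsening would be dropped even where the parameter has a table, and the gap would be larger.

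**The case against.** The best defence is that SAP Section 8 is itself current text and commits to a graded 28-day summary. Section 8.2 might then add a narrower shift display on top of it, with table shells (not in these documents) showing grades in the by-visit tables. On that view the two sections are merely unreconciled. Late worsening also has other outlets. Unsolicited AEs are identified partly from laboratory review and reported by severity through 28 days, and protocol 8.5 requires results of Grade 3 or above to be confirmed. The SAP covers only an interim analysis, so the protocol's requirement still stands for the final one. On the parameter-level reading, a single early worsening brings the whole parameter in.

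Some of this stands. The values are not lost, any omission at this interim can be recovered later, and the parameter-level reading keeps the gap narrower.

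The conflict remains. SAP 8.2 specifies the laboratory outputs and describes no other graded one, and shells that are not available cannot be assumed to supply it. The where-relevant qualifier most naturally refers to parameters that have a grade and does not shorten the 28 days. The AE route is incomplete by design, since protocol 9.5.1 says "Laboratory abnormalities deemed not clinically significant (NCS) by the Investigator should not be reported as AEs". Confirmatory retesting is monitoring and produces no table. The filing rests on the interim output, so later recovery in the final analysis does not help it.

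**Conclusion.** The concern holds. SAP 8.2 contradicts SAP Section 8 and protocol 10.5.3, and as written it reports a primary endpoint incompletely by grade. Two of the three post-dose chemistry and hematology draws cannot bring a parameter into the shift tables, and the third does so only on some of its permitted days.

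The 67% describes the entry condition. It is not the share of abnormalities missed, which the documents do not allow anyone to estimate. The conclusion assumes that the outputs named in SAP 8.2 are the laboratory outputs that will be produced, and it takes the narrower, parameter-level reading of the filter. It concerns this interim analysis. It should be corrected, and the correction is small.

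**What to change.** In SAP 8.2, replace the 7-day condition with worsening at any post-vaccination assessment through 28 days (the Day 29 visit), and cap the maximum grade at the same visit. The simplest form is one table per graded parameter, baseline grade against maximum post-baseline grade through Day 29, with no entry condition. That delivers the by-grade summary the endpoint asks for and removes both the day-count question and the doubt about whether the filter acts on parameters or participants. Shifts by visit are optional.

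Timing matters, because SAP 5.1 states: "No changes will be made to this interim analysis SAP after the data is pulled for analysis". If the data have not been pulled, the cost is one phrase and a wider date filter. If they have, add the table as a documented additional analysis and say why. All the results needed are already scheduled for collection.

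If the 7-day limit was intended, it should be listed in SAP Section 4 with its reason, and a separate 28-day graded summary should be specified so that the endpoint is still met.
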